	Day -12 to -5	Day 1	8 days ±2 after A1/A3/B3/C3	14 days ±2 after A1/A3/B3/C3	13 days ±2 after D3/down- titration ¹⁹	27 days ±2 after D3/down- titration ¹⁹	41 days ±2 after D3/down- titration ¹⁹	14 days ±2 after MPV3/EDV	14 days ±2 after last IMP intake
on-site visit ☒ / telephone contact ☎	☒	☒	☎	☒	☒	☒	☒	☎	☒
Right heart catheterisation ^{16,22}		●					● ⁸		
Blood withdrawal biomarker	●						● ⁸		

- EDV = early discontinuation visit. An EDV has to be performed within 10 days of early discontinuation. Additionally, patients who will not participate in the extension study will be contacted by phone at the time of last patient's last visit (LPLV) to document their vital status.
- Patients will be hospitalised for 24 hours.
- The dose will be increased if the previous dose was considered safe by the investigator according to safety criteria (at A3, B3 and C3).
- Blood samples for PK and PD to be taken prior to IMP intake as well as 1, 2, 4, 8, 16 and 24 hours after IMP intake (but still prior to next IMP intake).
- The patient has to be advised not to take the IMP at home on the day of A3, B3, C3, D3, MPV1, MPV2 and MPV3.
- Only in women of childbearing potential.
- Only applicable in patients taking 150 mg or 200 mg zamicastat and who will not participate in the extension study. In case a patient will discontinue the study early due to the occurrence of an AE, down-titration is not mandatory, but at the investigator's discretion.
- Not applicable at EDV.
- Visits during the Dose-finding period:
 - Dose A (50 mg zamicastat):** visits A1, A2 and A3
 - Dose B (100 mg zamicastat):** visits B2 and B3. These visits will only be performed if the patient was up-titrated to 100 mg zamicastat at A3.
 - Dose C (150 mg zamicastat):** C2 and C3. These visits will only be performed if the patient was up-titrated to 150 mg zamicastat at B3.
 - Dose D (200 mg zamicastat):** D2 and D3. These visits will only be performed if the patient was up-titrated to 200 mg zamicastat at C3.
 If the patient's next dose will not be tolerated, the patient will be asked to come to an unscheduled visit (UV) and he/she will be down-titrated to his/her previous dose.
- In scleroderma patients only.
- Blood pressure and heart rate will be measured in supine position (two measurements) and afterwards in standing position (one measurement).

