9.4.2 Withdrawals

Patients who have been enrolled and, for whatever reason, discontinue the study after first IMP intake at visit A1 are classified as withdrawals. Patients may withdraw from the study at any time, either on their own request or at the discretion of the investigator.

Reasons for withdrawal must be documented carefully in the patient's medical records and in the eCRF. Investigators must attempt to contact patients who fail to attend scheduled visits by telephone, letter, visit, etc., to exclude the possibility of an AE being the cause. Should this be the case, the AE must be documented, reported and followed up as described in Section 12. Attempts to contact the patient must be documented in the patient's medical records. The project leader and the medical monitor of the study at Bial will be informed of each withdrawal and the reason for it. To minimize the loss to follow-up, the specified patient's family member/friend (if available) will be contacted. An early discontinuation visit (EDV) (see Section 11.6.7) should be performed within 10 days, if possible, on each withdrawal. However, in case of early discontinuation due to withdrawal of consent, the patient will have the right to refuse this additional visit and phone calls and no further data will be collected for this patient apart from the reason for discontinuation. The investigator should attempt to retrieve all IMPs from all patients.

Patients may withdraw or may be withdrawn from the study for the following reasons:

- At their own request (withdrawal of consent)
- If in the investigator's opinion, for reasons of safety or ethics, continuation in the study would be detrimental to the patient's well-being
- Pregnancy
- Ineligibility/development of an exclusion criterion
- In case of an intolerable adverse event(s)
- At the specific request of the sponsor
- Lost to follow up
- Other reasons

Patients who are withdrawn are not to be replaced.

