11.6.9 Follow-up visit (FU, 14 days \pm 2 after last IMP intake)

This visit will be performed in all patients who will not participate in the extension study as well as in patients who discontinued early. The following assessments will be performed:

- Concomitant medication
- IMP accountability, only applicable in patients who were down-titrated
- AEs
- Vital signs* (blood pressure, heart rate and tympanic body temperature; blood pressure and heart rate will be measured twice in supine position and afterwards once in standing position)
- 12-lead ECG*
- Urine pregnancy test, in women of childbearing potential
- Blood withdrawal (haematology, coagulation and biochemistry)
- Urinalysis

*Painful procedures should be performed only afterwards.

11.7 **Unscheduled Visits**

Unscheduled visits can be performed as on-site visit or as telephone contact at any time during the trial for any reason. If a visit outside of the protocol evaluation time points is performed, the eCRF form for unscheduled visits will be completed.

The following assessments will be at least performed:

- Concomitant medication
- AEs

Additional examinations and blood sampling may be performed as deemed necessary by the investigator.

If the patient's next dose will not be tolerated, the patient will be asked to come immediately to an on-site visit or call the investigator and the dose will be down-titrated to the patient's previous tolerated dose. The reason for down-titration has to be documented in the source data and eCRF.

Patients who will not continue in the extension study will be contacted by phone at the time of LPLV to document their vital status. If it is not possible to contact the patient, the specified

patient's family member/friend (if available) will be contacted. If a patient died the date of death has to be documented in the source data and eCRF.

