Table 15.3.2.1.1.2 Summary of Clinical Laboratory Tests: Haematology – Safety Set

Table 15.3.2.1.2.1 Summary of Clinical Laboratory Tests: Biochemistry by HTD – Safety Set

Table 15.3.2.1.2.2 Summary of Clinical Laboratory Tests: Biochemistry – Safety Set

Table 15.3.2.1.3.1 Summary of Clinical Laboratory Tests: Coagulation by HTD – Safety Set

Table 15.3.2.1.3.2 Summary of Clinical Laboratory Tests: Coagulation – Safety Set

The default summary statistics of clinical laboratory test results will be presented by HTD and overall at V1, A3/B3/C3/D3, MPV1, MPV3/EDV and FUV2. The absolute change from baseline will be presented as well.

Table 15.3.2.1.4 Summary of Clinical Laboratory Tests: Urinalysis – Safety Set

Number and percentage of patients will be displayed by HTD and overall at V1, A3/B3/C3/D3, MPV1, MPV3/EDV and FUV2. Percentage will be based on the number of patients at the specified visit.

Table 15.3.2.2.1 Clinical Laboratory Tests: Incidence of Haematology Abnormalities – Safety Set

Table 15.3.2.2.2 Clinical Laboratory Tests: Incidence of Biochemistry Abnormalities – Safety Set

Table 15.3.2.2.3 Clinical Laboratory Tests: Incidence of Coagulation Abnormalities – Safety Set

Number and percentage of patients for each laboratory parameter will be displayed by HTD and overall in Low, CS Low, Normal, High and CS High categories. Percentage will be based on the number of patients at specified visit.

Table 15.3.2.2.4 Clinical Laboratory Tests: Incidence of Urinalysis Abnormalities – Safety Set

Number and percentage of patients for each laboratory parameter will be displayed by HTD and overall in Normal, Abnormal and CS abnormal categories. Percentage will be based on the number of patients at specified visit.

Table 15.3.2.3.1 Clinical Laboratory Tests: Shift Table of Haematology Results – Safety Set

Table 15.3.2.3.2 Clinical Laboratory Tests: Shift Table of Biochemistry Results – Safety Set

Table 15.3.2.3.3 Clinical Laboratory Tests: Shift Table of Coagulation Results – Safety Set

Shift tables showing changes in the number and frequency of patients with respect to the normal range between baseline and MPV3/EDV will be provided.

Table 15.3.2.3.4 Clinical Laboratory Tests: Shift Table of Urinalysis Results – Safety Set

Shift tables showing changes in the number and frequency of patients in Normal, Abnormal and CS abnormal categories between baseline and MPV3/EDV will be provided.

Listing 16.2.4.2.1 Laboratory Data: Haematology – Enrolled Set

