Table 15.3.5.3.1 Summary of Change in Short-Term IMP Effect on ECG Assessments by HTD – Safety Set

Table 15.3.5.3.2 Summary of Change in Short-Term IMP Effect on ECG Assessments – Safety Set

The changes from pre-dose values and the differences in changes from pre-dose values will be summarised between corresponding timepoints at visits A1 and MPV3 by HTD and overall.

Table 15.3.5.4.1 Incidence of ECG Abnormalities – Safety Set

Number and percentage of patients with Not CS abnormal and CS abnormal ECG parameters assessments will be displayed by HTD and overall. Percentage will be based on the number of patients at specified visit.

Table 15.3.5.4.2 Shift Table of ECG Abnormalities – Safety Set

Shift tables showing changes in the number and frequency of patients in not CS abnormal and CS abnormal categories between baseline and MPV3/EDV will be provided. The worst abnormality assessment collected during MPV3/EDV will be selected for each patient. Percentage will be based on the number of patients in the safety set.

Table 15.3.5.4.3 Shift Table of Within-Visit ECG Abnormalities – Safety Set

Shift tables showing changes in the number and frequency of patients in not CS abnormal and CS abnormal categories between the pre-dose measurement and each post-dose measurement at each visit.

The worst abnormality assessment collected during the corresponding timepoint will be selected for each patient. Percentage will be based on the number of patients in the safety set.

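### Laboratory shift Tables 15.3.2.3.1-4 and ECG Table 15.3.5.4.2 compare baseline with MPV3/EDV only, so a transient on-treatment abnormality can be tabulated as no shift

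*SAP*

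**What the plan says.** SAP 5.6.2 defines the shift tables for haematology, biochemistry and coagulation (15.3.2.3.1-3) in one sentence: "Shift tables showing changes in the number and frequency of patients with respect to the normal range between baseline and MPV3/EDV will be provided". For urinalysis, Table 15.3.2.3.4 does the same, using normal, abnormal and clinically significant abnormal categories. In SAP 5.6.5, ECG Table 15.3.5.4.2 shows shifts in abnormality "categories between baseline and MPV3/EDV will be provided", with this rule for repeated recordings: "The worst abnormality assessment collected during MPV3/EDV will be selected for each patient". Here the worst value means the worst within that one visit, not the worst on treatment. A second ECG table, 15.3.5.4.3, gives shifts "between the pre-dose measurement and each post-dose measurement at each visit".

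On the EDV, footnote 1 to the protocol's schedule of procedures states: "An EDV has to be performed within 10 days of early discontinuation". Protocol 9.4.2 is softer: the visit "should be performed within 10 days, if possible, on each withdrawal".

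On unscheduled visits, Protocol 11.7 requires only concomitant medication and adverse events, then adds: "Additional examinations and blood sampling may be performed as deemed necessary by the investigator". The laboratory summaries are "presented by HTD and overall at V1, A3/B3/C3/D3, MPV1, MPV3/EDV and FUV2", a list with no unscheduled visit. SAP 4.4 gives unscheduled visits their own labels, and SAP 4.8 has data analysed under the nominal visit number.

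SAP 4.3 presents visit-based safety output by HTD. Only adverse events and concomitant medications are summarised by the dose being taken at the time.

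**The concern.** Clinically relevant changes in laboratory and ECG parameters are named safety endpoints (Protocol 13.1.2.1), and ECG changes are among the up-titration criteria. The patients who say most about tolerability are those who could not stay on a dose, and the design moves them away from that dose before the shift tables look at them. Intolerance of 50 mg, or of the HTD during maintenance, means withdrawal and an EDV. Intolerance of a higher dose means stepping back to the previous dose for the 42-day maintenance period. In either case the on-treatment abnormality may have resolved by the comparison visit, and the patient is then counted as unchanged. A reader using the shift tables to judge laboratory and ECG safety would see too few shifts, and would see them under the wrong dose.

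**Working it through.** The plan states no figure on this point, so there is none to reproduce. The check sets the visit schedule against the table definitions.

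**1. Visits available and visits used.** Inputs: the schedule of procedures and SAP 5.6.2 and 5.6.5. The final follow-up visit is not counted, because it is set 14 days after last intake. In the lower three rows the next dose is stopped between scheduled visits.

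| Course | Laboratory visits after first dose | ECG visits (adds A1 and MPV2) | Used by the shift table |
|---|---|---|---|
| HTD 200 mg | A3, B3, C3, D3, MPV1, MPV3 = 6 | 8 | 1 |
| HTD 150 mg | A3, B3, C3, MPV1, MPV3 = 5 | 7 | 1 |
| HTD 100 mg | A3, B3, MPV1, MPV3 = 4 | 6 | 1 |
| HTD 50 mg | A3, MPV1, MPV3 = 3 | 5 | 1 |

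In the lower three rows no scheduled laboratory or ECG visit falls at the non-tolerated dose. An optional unscheduled sample may be the only result there. SAP 5.6.5 notes that patients enrolled under protocol version 1.0 had no ECG at A1 or MPV2, so their ECG maximum is 6.

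**2. Down-titrated completers.** MPV3 is set 41 ± 2 days after down-titration: 41 − 2 = 39 and 41 + 2 = 43. The compared value is therefore taken 39 to 43 days after the non-tolerated dose was left, at a lower dose. Under SAP 4.3 it is shown in the lower HTD group.

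**3. Withdrawn patients.** The 10 days run from early discontinuation, not from last intake, and apply where possible. SAP 4.6 makes the EDV date the end of any ongoing study period. The shift tables pool EDV with on-treatment MPV3, with no flag for days since last intake.

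**4. Unscheduled results.** Three SAP statements read together: analysis is by nominal visit, unscheduled visits carry separate labels, and the shift endpoint is MPV3/EDV. On that reading an unscheduled result does not enter these tables. This is an inference, since the SAP has no explicit rule.

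**5. Table 15.3.5.4.3.** Post-dose ECGs are scheduled only at A1, on 50 mg, and at MPV3, on the HTD. This table cannot recover an abnormality at a higher dose that was later abandoned.

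**6. Illustration of masking.** Both inputs are assumptions. Suppose k of the 32 planned patients have an on-treatment abnormality, and each is independently back in the baseline category at MPV3/EDV with probability r. Then the expected proportion shown is k(1 − r)/32, and the probability that none is shown is r^k. For k = 4, the proportion with an abnormality is 4/32 = 12.5%:

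| r | Expected shown | P(none shown) |
|---|---|---|
| 0.25 | 4 × 0.75/32 = 9.4% | 0.25^4 = 0.004 |
| 0.50 | 4 × 0.50/32 = 6.25% | 0.50^4 = 0.06 |
| 0.75 | 4 × 0.25/32 = 3.1% | 0.75^4 = 0.32 |
| 0.90 | 4 × 0.10/32 = 1.25% | 0.90^4 = 0.66 |

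At r = 0.50, k = 2 gives 3.1% shown against 6.25% affected, and k = 6 gives 9.4% against 18.75%.

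**The case against.** A shift from baseline to end of treatment is a legitimate choice in a descriptive study of 32 patients. Protocol 13.4.3 promises counts and percentages of clinically relevant abnormalities, not shift tables, and the SAP delivers those counts in the incidence tables with clinically significant categories. Protocol 12.1.1 has abnormalities recorded as adverse events when they are clinically significant or change the patient's schedule. Those events are tabulated by the dose at onset, including events leading to down-titration or discontinuation, and an event starting on the day of down-titration goes to the previous dose. All of this stands, and it limits the point to the shift tables.

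Several stronger readings are tempting, and the documents do not support them:

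- **That the safety signal is lost.** Adverse event tables and listings should show a clinically significant abnormality, as should the incidence tables if it was seen at a scheduled visit.
- **That the EDV is taken up to 10 days off drug.** The clock starts at discontinuation and applies where possible, so time off drug may be shorter or longer. SAP 4.6 also lets down-titration begin the day after EDV, so some patients may still be dosing at that visit.
- **That unscheduled results are excluded by rule.** The SAP is silent, and the table shells are not available. Intolerance may also be found at a scheduled visit, and an unscheduled contact may be a telephone call that yields no sample.
- **That these are the only within-patient categorical comparisons.** Table 15.3.5.4.3 is another.
- **That residual drug at EDV measures the harm.** The documents give no half-life, describe the pharmacokinetics as time-dependent, and do not link clearance of drug to resolution of an abnormality.

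The other outputs do not fully replace the shift. Incidence tables are cross-sectional, with visit-based denominators, and are grouped by final HTD. Where an abnormality is a sign of a condition, the condition is reported as the adverse event and not the sign.

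**Conclusion.** The point holds as a reporting gap in Tables 15.3.2.3.1-4 and 15.3.5.4.2. They use one of up to 6 laboratory or 8 ECG visits, and that visit comes after the design has moved intolerant patients to a lower dose or off treatment. An abnormality that has resolved by then is tabulated as no shift. For a down-titrated completer, this happens under the lower HTD.

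The visit counts and the 39-to-43-day interval follow directly from the schedule. The exclusion of unscheduled results is an inference from nominal-visit analysis. The number of patients affected is unknown, and the masking figures only illustrate assumed inputs. Sample size and error rates are not touched. This is a cheap improvement to the reporting of a named safety endpoint.

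**What to change.** For the laboratory shift tables and ECG Table 15.3.5.4.2:

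- Add a shift from baseline to the worst on-treatment value, taken from all scheduled and unscheduled results between first and last IMP intake. State in the SAP that unscheduled results count.
- Show it by dose at the time of assessment as well as overall. By HTD alone, an abnormality at an abandoned dose would still sit under the lower one. A result taken at a titration visit before the new dose is taken belongs to the dose just completed. For the day of down-titration, the adverse event rule in SAP 5.6.1 can be reused.
- Keep the baseline-to-MPV3 shift for completers.
- Show EDV values separately, or flag them by EDV date minus last IMP intake date.

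The cost is SAP wording and programming, with no new data collection. The downside is that a worst value draws on more visits and will show somewhat more abnormality by chance. The retained MPV3 shift puts that in context.

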#### Listing 16.2.4.2.6 Laboratory Data: Pregnancy Tests – Enrolled Set

Data of pregnancy tests will be listed.

### **5.6.3 Arterial Blood Gas Analysis**

Arterial blood gas analysis will be performed at visit A1 and MPV3 before first IMP intake.

The following parameters of Arterial blood gas analysis will be collected:

- Fraction of inspired oxygen (%) (**FiO2**)
- pH
- oxygen partial pressure (mmHg) (**pO2**)
- carbon dioxide partial pressure (mmHg) (**pCO2**)
- bicarbonate (mEq/L)
- base excess (mEq/L) (**BE**)
- arterial oxygen saturation (%) (**SaO2**)\*
- sodium (mEq/L)
- potassium (mEq/L)
- lactate (mEq/L)

\* - Collected as “O2 content (%)” in earlier eCRF versions.

If arterial blood gas analysis is not performed, then peripheral oxygen saturation (%) will be collected.

The clinical significance (yes/no) of any abnormal Arterial blood gas analysis findings will be assessed by the investigator. Parameter values without a clinical significance evaluation will be considered as “Normal”, and values with “No” or “Yes” clinical significance evaluations will be considered as “NCS Abnormal” and “CS Abnormal”, respectively.

The following statistical output will be provided:

#### Table 15.3.3.1.1 Summary of Arterial Blood Gas Analysis by HTD – Safety Set

#### Table 15.3.3.1.2 Summary of Arterial Blood Gas Analysis – Safety Set

The default summary statistics of Arterial blood gas analysis parameters will be presented by HTD and overall at visits A1 and MPV3. The absolute change from baseline will be presented as well. For the changes from baseline a 95% confidence interval will be provided.

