## 4.7 Baseline Value

### Baseline value

The baseline value for a variable is defined as the last non-missing value collected before the first IMP intake, unless otherwise specified.

See section 5.4.1 Exposure to IMP for definition of first IMP intake.

**Absolute change from baseline** will be calculated as

$$\text{Absolute Change from Baseline at Visit } X = \text{Value at Visit } X - \text{Baseline Value}$$

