### 5.5.2 6-Min Walk Test (6-MWT)

The 6-MWT is a self-paced test of walking capacity used to assess aerobic capacity and endurance. It plays a key role in evaluation functional exercise capacity, assessing prognosis and evaluating response to treatment across a wide range of respiratory diseases. The distance covered over a time of 6 minutes is used as the outcome by which to compare changes in performance capacity.

The test will be performed at visit V1 before IMP intake and at visit MPV3 before right heart catheterisation.

At screening, two attempts must be performed, separated by at least 30 minutes. The attempt in which the longer distance was covered will be considered as baseline. In case the distance covered during both attempts is equal, the first attempt will be considered as baseline.

The following parameters will be collected:

- SpO2 (%) – before and after the test
- Borg Dyspnoea score – before and after the test
- Heart rate (bpm) – before and after the test
- Lap length (m)
- Number of laps completed
- Distance covered (m)
- Time walking (min)
- Oxygen flow rate (L/min)
- Number of stops
- Time stopped (min)

The Borg Dyspnoea score is a patient-reported measure for assessing breathlessness. Symptoms of breathlessness are rated on a scale of 0-10, where 0 indicates no symptoms and 10 indicates the most severe breathlessness.

The differences in SpO2, the Borg Dyspnoea score, and heart rate between after and before the test will be calculated. These differences will be displayed as additional parameters in summaries.

The following statistical output will be provided:

Table 15.2.2.1 Summary of 6-MWT by HTD – Full Analysis Set

Table 15.2.2.2 Summary of 6-MWT – Full Analysis Set

Table 15.2.2.3 Summary of 6-MWT by HTD – Modified Full Analysis Set

Table 15.2.2.4 Summary of 6-MWT – Modified Full Analysis Set

The default summary statistics of 6-MWT test results will be presented by HTD and overall at visits V1 and MPV3. The absolute change from baseline will be presented as well. For the changes from baseline a 95% confidence interval will be provided.

Table 15.2.2.5 Summary of 6-MWT Distance – Modified Full Analysis Set (TAPSE Subgroups)

The default summary statistics of 6-MWT distance travelled will be summarised by TAPSE subgroup and overall at visits V1 and MPV3. The absolute change from baseline will be presented as well. For the changes from baseline a 95% confidence interval will be provided.

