#### Table 15.3.3.4.1 Summary of Peripheral Oxygen Saturation (%) by HTD – Safety Set

#### Table 15.3.3.4.2 Summary of Peripheral Oxygen Saturation (%) – Safety Set

The default summary statistics of peripheral oxygen saturation (%) will be presented by HTD and overall at visits A1 and MPV3. The absolute change from baseline will be presented as well. For the changes from baseline a 95% confidence interval will be provided.

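### Change in arterial pO2 and SaO2 is summarised as a raw difference with no within-patient link to the recorded FiO2, so a change in oxygen supply can mask or mimic a change in gas exchange

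*SAP*

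**What the plan says.** Both documents list clinically relevant change in laboratory parameters, including arterial blood gas analysis, as a secondary safety endpoint (protocol 13.1.2.1, SAP 2.2.2.1). SAP 5.6.3 collects "Fraction of inspired oxygen" (in percent) together with oxygen partial pressure, "arterial oxygen saturation" and the other gas parameters at A1 and MPV3.

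For Tables 15.3.3.1.1 and 15.3.3.1.2 the SAP states: "The default summary statistics of Arterial blood gas analysis parameters will be presented by HTD and overall at visits A1 and MPV3". It continues: "The absolute change from baseline will be presented as well. For the changes from baseline a 95% confidence interval will be provided". SAP 4.7 defines that change as the visit value minus the baseline value, with no other term. Where a blood gas is not done, peripheral saturation is collected instead and handled in the same way in Tables 15.3.3.4.1 and 15.3.3.4.2: "The default summary statistics of peripheral oxygen saturation (%) will be presented by HTD and overall at visits A1 and MPV3".

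Protocol 11.3.2 sets the blood source and the timing of the sample. It does not ask for room air or for the same inspired oxygen at both visits, and its list of blood gas parameters does not name FiO2. The eligibility criteria (protocol 9.2 and 9.3) and the prohibited therapies (10.8.2) do not mention supplemental oxygen. The walk-test data in SAP 5.5.2 include an oxygen flow rate, so oxygen use is foreseen.

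**The concern.** At a given state of gas exchange, pO2 and SaO2 depend on how much oxygen the patient is breathing. A visit-minus-baseline difference reflects gas exchange alone only if inspired oxygen is the same on both occasions. Here that is neither required nor checked in any planned table, although the variable needed to check it is on the SAP's list.

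A patient whose gas exchange worsens and who is on more oxygen at MPV3 may contribute a zero or positive change to the mean. A patient who improves and is on less oxygen may contribute a zero or negative one. In either case the reader of a safety table cannot separate the two components. The tables by highest tolerated dose (HTD) are the most exposed, because one or two patients can move the mean of a small group.

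The SAP recognises the same kind of problem for efficacy, where the modified full analysis set excludes patients with substantial changes in PAH-approved drugs or diuretics. That rule does not cover oxygen, and safety is analysed on the safety set.

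**Working it through.** There is no figure in the plan to reproduce: the sample size of 32 was not formally calculated, and no mean, SD or FiO2 distribution is given for blood gases. The check is a reading of the text followed by an illustration.

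**Reading.** FiO2 is collected (SAP 5.6.3). Change is value minus baseline (SAP 4.7). The blood gas tables apply that definition with a 95% CI (SAP 5.6.3). Neither document contains a pO2/FiO2 ratio, an alveolar-arterial gradient, a stratification by FiO2, or a rule for patients whose oxygen differs between visits.

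**Illustration.** All gas values are assumptions. Baseline is 65 mmHg on FiO2 0.21, so pO2/FiO2 = 65/0.21 = 310. SaO2 changes use the Severinghaus curve.

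| pO2 and FiO2 at MPV3 | Raw change in pO2 (mmHg) | Change in SaO2 (points) | pO2/FiO2 at MPV3 | Change in pO2/FiO2 |
|---|---|---|---|---|
| 65 on 0.24 | 0 | 0.0 | 271 | -39 |
| 70 on 0.24 | +5 | +1.4 | 292 | -18 |
| 80 on 0.24 | +15 | +3.3 | 333 | +24 |
| 75 on 0.28 | +10 | +2.5 | 268 | -42 |
| 90 on 0.32 | +25 | +4.5 | 281 | -28 |

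The two measures can disagree in sign (rows 2, 4 and 5), the raw change can be zero while the ratio falls (row 1), or both can rise (row 3).

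**Break-even.** The ratio is unchanged when pO2 at MPV3 = (65/0.21) × FiO2 at MPV3. That is 74.3, 86.7 and 99.0 mmHg at 0.24, 0.28 and 0.32. From this baseline, raw gains of up to about 9, 22 and 34 mmHg are compatible with a lower ratio.

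**Effect on a group mean.** Take two patients who move from 65 on 0.21 to 75 on 0.28, with all others unchanged.

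- Raw change per patient: 75 − 65 = +10 mmHg.
- Room-air equivalent per patient: (75/0.28) × 0.21 − 65 = 56.25 − 65 = −8.75 mmHg.
- Among 32: raw 2 × 10/32 = +0.6 mmHg; room-air equivalent 2 × (−8.75)/32 = −0.5 mmHg.
- In an HTD group of 8 (assumed size): raw 2 × 10/8 = +2.5 mmHg; room-air equivalent 2 × (−8.75)/8 = −2.2 mmHg.

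The figure of 32 supposes that every planned patient has a blood gas at both visits.

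**The case against.** The strongest reply is that the raw-change table is one display among several.

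- FiO2 is itself a listed parameter, so its mean and change would appear in the same tables.
- Listing 16.2.4.3 gives individual values, readable for about 32 patients.
- The endpoint is worded as clinically relevant change, and Tables 15.3.3.2 and 15.3.3.3 use the investigator's assessment, which can take oxygen into account.
- Abnormalities that are clinically significant or need treatment are to be recorded as adverse events (protocol 12.1.1).
- The study is single-arm and descriptive, and no decision rule rests on mean pO2.

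All of this stands, and it limits the weight of the point. It does not close the gap. A mean FiO2 beside a mean pO2 does not show whether the same patients moved on both. The investigator-rated tables have no FiO2 rule, and a value with no significance evaluation counts as normal. A listing is not a summary.

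Two stronger readings are tempting. A reader might infer that the bias favours the drug, because patients who worsen are the ones given more oxygen. The documents do not show this: they do not say that any patient's oxygen changed, a reduction would bias the other way, and entry required 90 days of stable PAH therapy.

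A reader might also size the problem from the alveolar gas equation: 0.07 × 713 = about 50 mmHg for a move from 21% to 28%, hence 1.6 to 4.7 mmHg in the mean of 32 for one to three patients. That assumes an unchanged alveolar-arterial gradient, so it does not describe patients whose gas exchange worsened.

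**Conclusion.** The point holds as a weakness of the planned summary. Change in pO2 and SaO2 is not linked to FiO2 within patient, and constant inspired oxygen is not required, so the raw change can mislead in either direction when oxygen supply differs between A1 and MPV3. It does not follow that a worsening will be reported as an improvement.

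The actual size is unknown and could be nil, because the documents give no count of patients whose oxygen changed. On the assumed values above, a few such patients have a small effect on the overall mean and a larger one within a small HTD group, where the sign can differ from that of an oxygen-adjusted measure. The ratio pO2/FiO2 is a simple index of oxygenation relative to supply, not a full correction. This is an inexpensive improvement, not the repair of a contradiction.

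**What to change.** In SAP 5.6.3:

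1. For all safety-set patients with pO2 and FiO2 recorded at both A1 and MPV3, derive pO2/FiO2 (with FiO2 converted from percent to a fraction). Summarise its change with a 95% CI, by HTD and overall.
2. Count, by HTD and overall, the patients whose FiO2 at MPV3 was higher, the same, lower or not recorded relative to A1, and flag them in Listing 16.2.4.3. If no FiO2 differs and none is missing, this count supports the raw blood gas tables as they stand.
3. Keep the existing change tables for pO2, SaO2 and peripheral saturation, with a footnote that they are not corrected for inspired oxygen.

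A summary restricted to patients with the same FiO2 at both visits may be added only as supportive, beside items 1 and 2. It selects on a post-treatment variable and can drop the patients who worsened.

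The cost is one derived variable, one count table and some wording. There are limits. FiO2 may be missing for some patients, since the protocol's blood gas list does not name it. The ratio does not correct SaO2, and SAP 5.6.3 specifies no oxygen setting for the peripheral saturation substitutes. No change to oxygen treatment is proposed.
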